Training target: Consistent with the experimental therapeutics approach, we will not only evaluate outcomes of interest, but also the potential impact of the intervention on the hypothesized treatment mechanism. In this case, we hypothesize the mechanism to be social cognitive skill, indexed by learning of content taught during USS. Hence, we will use the USS Skills Test to index target engagement. The USS Skills Test is a 22-item measure assessing knowledge of principles and skills taught during the training⁵⁴. Items on the USS Skills Test are similar to (though not identical) to those used in the USS training stimuli, and as such, should provide a proximal measure of training effects. Our pilot data indicates that the USS Skills Test is sensitive to training effects.

Measures for normative psychiatric (non-psychotic) sample:

Veterans in the psychiatric subgroup will be asked to complete a subset of measures administered to the psychosis sample and described above, specifically: background/demographic information, Social Functioning Scale (SFS), Patient Health Questionnaire-9 (PHQ-9), the Social Skills Performance Assessment (SSPA), and a baseline Ecological Momentary Assessment (EMA). Psychiatric diagnosis will be confirmed via psychiatric interview, using the Structured Clinical Interview (SCID) as needed.

[figure not shown]
Interventions (only administered to psychotic-spectrum sample):

Experimental intervention, Understanding Social Situations (USS):

USS was developed by the PI and collaborator [name] under an NIMH R34 grant. It was developed to train higher-order social cognitive skills. Training content was largely adapted from successful lab-based experimental interventions targeting theory of mind and attributional bias. Given that significant cognitive impairments in people with psychosis can limit skill acquisition, USS was uniquely developed to lessen cognitive load by relying on delivery techniques that have previously been successfully used in cognitive remediation including scaffolding, hierarchical training, massed drill and practice, performance-based increases in task difficulty, and verbal mediation.

Additional techniques include motivational enhancement and use of homework to promote bridging to real-world situations. Complex skills are trained by first practicing their individual components. There are four training modules (see below) that are administered over 8-10, individual, hour-long sessions. Training stimuli consist of photos, videos, cartoons, written vignettes, and audio clips of mostly social situations. Once participants complete the four USS modules, all training content will again be reviewed. This approach mirrors many real-world clinical setting where Veterans undergo multiple cycles of an intervention, is intended to further compensate for cognitive impairments, and is intended to assure that training content is learned and consolidated. In total, participants will be asked to undergo 16-20 USS sessions over 2 months.

Figure 1. Graded increases in task difficulty

UNDERSTANDING SOCIAL SITUATIONS (USS) TRAINING

Techniques employed throughout USS content include hierarchical training, massed drill and practice, breaking skills into subcomponents, graded increases in task difficulty, scaffolding, errorless learning, verbal mediation, modeling, minimizing memory load via visual cues, and use of homework to promote bridging to real-world situations. The first three USS modules contain hierarchical difficulty levels, with

task difficulty manipulated by adjusting response format, plausibility of foils, stimulus ambiguity, valence, self-relevance, etc. Progress through the training is tailored to individual performance in order to provide an optimal level of challenge while minimizing frustration. Sessions are highly structured and include homework, review of prior session's content, modeling and practice of new skills, and assignment of new homework.

Psychoeducation and motivation enhancement: The trainee is provided with a rationale for engaging in the ensuing training (to better understand social situations which will help in getting along well with others). Brief video vignettes of social problems are reviewed and the trainee's own experiences with situations where s/he had difficulty figuring out what the other person was thinking or feeling are discussed. The trainee identifies a specific goal pertaining to his or her social life. An overview of the skills to be trained is provided.

Module 1 Separating Facts from Guesses: Training focuses on distinguishing between observable behavior and inferences about thoughts, feelings and social meanings. Training progresses from identifying what are tangible facts, and distinguishing them from guesses, particularly about others' mental states. Training further progresses to distinguishing between good, fact-based guesses versus bad guesses that have little or no support. (Techniques adapted from Social Cognition Interaction Training, SCIT; [name] & Penn^{55, 56}).

Module 2 Probability Judgments and Not Jumping to Conclusions: Training focuses on developing skills to evaluate the quality of guesses based on how much information is available to support guesses. Training progresses from rating guesses as good or bad, to rating the relative likelihood of multiple guesses about a single situation, to re-rating quality of different guesses as more information is provided about the situation (techniques adapted from Moritz & Woodward⁵⁷).

Module 3 Determining Others' Mental States and Intentions: Training focuses on using verbal mediation to process temporal sequences of social events and identify information in support of various guesses about a character's current or future intentions. Training progresses from evaluating individual stimuli to integrating information from multiple stimuli to making guesses about characters' mental and emotional states and intentions (techniques adapted from Sarfati and colleagues^{58, 59}).

Module 4. Inducing Positive Interpretive Bias: Cognitive bias modification training. Goal of this module is for trainees to develop an automatic bias toward interpreting ambiguous social events in a positive manner. Trainees practice by completing very brief written stories about themselves in social situations, with each story resolving in a favorable way. Unlike other modules, there are no difficulty levels (techniques adapted from Constans and colleagues^{60, 61}).

Matched Active Control intervention (AC):

The active control (AC) intervention was selected to match USS on interaction with study staff, treatment duration and intensity, and delivery format. "Moving Forward: Overcoming Life's Challenges" is a free, web-delivered training developed by the VA as part of the Integrated Mental Health Strategy initiative to expand access, ensure quality of care, promote resilience and build better behavioral health systems. The training is based on Problem Solving Therapy⁸⁰, an evidence-based cognitive-behavioral approach to developing problem solving skills to effectively cope with stressors⁸¹. It consists of 8 modules focused on what the training is, how it may be helpful, how to solve problems under stress, steps of problem solving, and how to apply what was learned to daily life. In preparation for the current grant submission, we thoroughly reviewed and timed module content, developed procedures for how this normally self-administered program can be delivered by a study trainer in 45-60 minute sessions, and created a training manual (see Appendix). Similarly to those in the USS condition, participants in AC condition will be asked to attend two cycles of the training, for a total of approximately 16-20 sessions over two months.

Procedures for psychotic spectrum sample: Please refer to the study design and the assessments timeline (above) for detailed schematics of study procedures and assessments. Following written informed consent and baseline assessment, Veterans will be randomized (1:1) into one of two training conditions: Understanding Social Situations (USS) or a matched Active Control (AC). Training sessions will occur approximately twice per week for two months (16-20 sessions, given some expected variability in individual time to complete the training content). Training sessions will be video recorded for later fidelity ratings by research staff.

Comprehensive assessments will be conducted at baseline and repeated at two months (end of active phase), and four months (two-month follow-up from end of active phase). An additional assessment for the primary outcome (SFS) and hypothesized moderator (USS Skills Test) will occur at one month (midpoint through the active phase). Participants will be oriented to the EMA procedures during the baseline assessment. This will include practice with receiving EMA survey links, navigating the questionnaires, and a comprehension check of survey questions and responses. Smartphones will be given to participants so that they can complete these EMA surveys. In addition to the smartphones, a data plan will be provided for 6-months or until study completion. Participants will then be provided with instructions for how to transfer the phone service into their name if they wish to keep the phone. For participants who are terminated for cause or decide to withdraw from the study, the dataplan will be terminated and the phone will be locked to prevent it being used to obtain a new wireless service plan. Orientation, including basic use and charging of the smartphone will be provided when the phones are given out. We anticipate that length of study participation for individual participants will be approximately 5 months.

Procedures for normative psychiatric (non psychotic) sample: Following written informed consent and baseline screening assessment using measures described above (approximately 90 min session), participants who continue to meet all eligibility criteria will be oriented to the EMA procedures. This will include practice with receiving EMA survey links, navigating the questionnaires, and a comprehension check of survey questions and responses. Participants will be asked to save to their contacts the telephone number from which the surveys originate. Next, over the course of 7 days they will receive 4x/day brief surveys about their social interactions. Survey questions are the same as for the psychosis spectrum sample. Length of study participation for the normative sample is approximately 7 days (baseline screening assessment plus 7 days of EMA assessments).

COVID-19 Pandemic Procedures: As long as COVID-19 remains a significant concern, this study will conduct the majority of research procedures remotely, via VA-approved telehealth platforms, for all participants recruited during the pandemic. Conducting as many procedures remotely as possible will help to reduce the length of time that in-person interactions are taking place and thus increase staff and participant safety during this pandemic.

Remote procedures: In the setting of the novel coronavirus pandemic, the consent form will be mailed to subjects after participating in a phone screening to determine initial eligibility. Upon receipt of the consent form, the consent form will be reviewed with the subject during a telehealth visit, signed and returned to the research team when the participant comes in for their in-person visit. The majority of the study assessments will be conducted using VA-approved video conference platform. Appointments conducted via video will not be recorded, with the exception of the USS/active control sessions, which are also recorded during in-person sessions, to allow for fidelity ratings to be conducted later.

Any virtual sessions will follow safety guidelines that are used in routine VA telehealth care, including the following:

1. Communicating to the participant the importance of having private space to ensure their confidentiality during study sessions
2. Determining an emergency contact, and the location/address of participant at the time of the study session
3. Using available elements of the video platform to ensure confidentiality (e.g., “locking” the virtual meeting room)

When administering assessments that measure depression or SI (PANSS, PHQ-9, or SCID) remotely, in addition to the safety precautions above, we will ensure that the PI is readily available. If the subject expresses SI, whoever is doing the assessment will contact the PI who will do a more detailed imminent risk assessment over the phone. If the PI believes there is risk and is concerned for the study participant's safety, 911 will be called for a welfare check.

In order to allow for remote administration and to limit in-person visits, some changes to the MCCB cognitive assessments have been made including:

- Eliminating spatial span, BVMT and mazes subtests
- Replacing the MCCB Symbol Coding with an oral version of the Symbol Digit Modalities Test,
- Using the oral version of Trails A and B instead of the standard version of the Trails A

In-person study visits conducted at baseline, post-training and follow-up time points will kept as brief as possible, and include the following safety guidelines:

- For any in-person visits that take place, one day prior to the visit and/or at time of visit, participants will be asked the standard COVID-10 screening questions in place at VACHS, and be asked to use a hand sanitizer upon entering the office.
- Participants will be required to wear a 2-ply face mask when in the room with research staff, and if they do not have one, one will be provided for them.
- Staff will utilize masks, gloves, face shields and social distancing during study visits, and will sanitize the office between each in-person visit and at the end of the day.

Recruitment: Veterans with and without psychotic spectrum diagnoses will be recruited from VACHS outpatient clinics via flyers, presentations of study to treatment teams, other research groups, and MH clinicians. The study will also be presented to Veterans during community meetings of the VACHS Psychosocial Rehabilitation and Recovery Center, which serves Veterans with serious mental illness. Recruitment will also

occur through our re-contact repository (those who have participated in our group's prior studies and agreed to be re-contacted with information about additional research opportunities), with the exception of those who participated in the initial USS treatment development trial. We may also pull MH clinic appointment lists, screen upcoming appointments for potential eligibility, alert providers to upcoming appointments with potentially eligible participants, and ask that they refer those who are interested in learning more about the study. We will also offer a small incentive to past/current participants who refer other eligible Veterans. For Veterans with psychotic spectrum diagnoses only, we may also send out study solicitation letters (with opt-out cards), as has previously been approved by the HSS.

Randomization for psychotic spectrum sample: Veterans who meet eligibility criteria and consent to study participation will be randomized to receive either USS or AC in a 1:1 ratio. Randomization will be stratified by baseline SFS score, using a permuted block design with variable block size. The randomization scheme will be computer-generated by the statistician and the allocation sequence will be concealed.

Payment for psychotic spectrum sample: \$50/each for baseline (\$25 for initial screening plus \$25 for subsequent baseline assessment), post-training and 2-month follow-up assessments; \$10 midpoint assessment; \$1/each EMA survey assessment (\$4/day); \$10/training session. Smartphones will be provided to all participants with 6-month data plans and the option to keep the phone at the conclusion of the study and transfer service into their name.

[figure not shown]
Payment for normative psychiatric control sample: \$25 for baseline screening assessment; \$1/each EMA survey assessment done within 1 hour of survey receipt (\$4/day over 7 days, for \$28 EMA maximum). Total study participation payment up to \$53.

Fidelity: In the full study, we will promote equipoise between the USS and AC conditions by describing the project to potential participants as evaluating the efficacy of two different trainings in improving quality of life. The success of this will be assessed at end of study participation, when participants will be asked to indicate whether they thought they received the experimental or control condition (dichotomous ratings). As detailed below, we are using an active intervention (with different treatment targets) for the control condition, hence expect that most participants will indicate they received an active, potentially efficacious treatment.

Data integrity and management: Data integrity is a process that begins with appropriate administration, scoring, and recording of results. All study staff will be trained on any new procedures. Data flow will be reviewed during weekly lab meetings. We will use VA RedCAP (Research Electronic Data Capture) for data collection and management for all but the EMA assessments. VA RedCAP is a web-based application, accessible only on VA network, and housed on the VA Informatics and Computing Infrastructure (VINCI) server. It was specifically designed for human subjects research, and includes multiple features to enhance data quality control, ease data entry, and assure data security. Because VA RedCAP survey links can only be accessed on VA intranet, to which study participants do not have access, we will use our Qualtrics to capture EMA data. Procedures for using Qualtrics for EMA data are in place, and have previously been approved by the VACHS IRB, Information Security Officer and Privacy Officer.

Statistical Analysis Plan:

Justification of Sample Size: The primary hypothesis is that USS will result in greater total SFS scores immediately following training (i.e. 'post' assessment) compared to control. We have powered our study to detect what we consider a clinically meaningful, moderate effect on this measure. Given the following: 1) power of 90%, 2) a two-sided 0.05 significance level, 3) a standard deviation for total SFS score of 13.1 (from our preliminary data), and 4) a 1:1 intervention allocation, a sample size of 46 subjects per group will be required to detect a 9 point difference (i.e. moderate effect size $d=0.69$) between USS and control in total SFS score at the post assessment. Please refer to Figure, showing the power to detect different effect sizes in total SFS given this sample size. A total of 120 participants will be enrolled and randomized to accommodate up to 20% dropout.

While inherently difficult to define as it varies by perspective (e.g. researcher, consumer, insurance company)⁸², we settled on moderate ES on SFS as clinically meaningful based on past social cognitive studies that used the SFS and noted that improvement in social relationships (more friends, less time spent alone, higher quality of social communication) were observed with small-medium effect sizes⁸³. Small-medium effects on the SFS have also been related to greater social acceptability by peers, better overall social skills ability, and higher medication compliance, with effects greater than 0.50 on social cognitive measures distinguishing between patients with psychosis and higher functioning patients with bipolar disorder⁸⁴. Perhaps the most striking example of the real-world significance of change on the SFS comes from the original SFS validation study, wherein 11 point difference separated those who were employed from those who were not⁷³.

General Approach: Nominal and ordinal categorical variables will be summarized using frequencies and percentages. Continuous variables will be summarized with the following descriptive statistics: N, mean, standard deviation, median, minimum, maximum, interquartile range, and range. No imputation of missing data will be performed in the primary and secondary analyses. Diagnostic tests and sensitivity analyses will be performed. Parametric distributional assumptions will be checked. If assumptions fail, other distributions will be considered prior to transformations and non-parametric methods. For all analyses, two-sided significance tests will be implemented and will be performed using SAS v9.4 (Cary, NC).

Comparability of Baseline Characteristics: Distributions of baseline demographic and clinical characteristics will be summarized. Comparability for continuous variables will be examined graphically and by summary statistics (means, medians, quartiles, etc.). Categorical variables will be examined by frequency distributions.

Analysis of Primary Outcome SFS (Aim 1): The primary objective of the analysis is to demonstrate that USS will improve social functioning at the end of training more than active control in participants with PSD and impaired social functioning. The primary outcome (total scores on the SFS) will be assessed prior to initiation of intervention (pre), the training mid-point (mid), the end of training (post) and 2 months following the end of training (FU). Likelihood-based ignorable analysis using a linear mixed model will be used to compare social functioning between groups^{85, 86}. The primary advantage of the repeated measures linear mixed model when compared to commonly used methods such as complete case analysis and single imputation (e.g. last observation carried forward) is its flexibility in handling missing data. This analysis will assume that missing data occurs at random (i.e. MAR, not informative). The inclusion of pre, mid and FU outcome data in the model will assist in meeting this assumption. Furthermore, we will evaluate patterns of missing data as well as determine baseline characteristics that are predictive of dropout. If identified, these characteristics will be included in the model to meet the MAR assumption. The mixed model will include fixed effects for intervention (USS vs. active control), time (mid, post, FU), and the interaction of intervention with time. An additional fixed effect will be included for baseline SFS at pre. An unstructured covariance pattern will be used to accommodate correlation from repeated measures. A linear contrast will be used to estimate intervention group differences and 95% confidence intervals at the post assessment.

Analysis of Real World Social Behaviors (Aim 2): Ecological momentary assessment (EMA) analyses will be conducted using a multilevel modeling approach⁸⁷. Analyses handle data estimation with a restricted maximum likelihood approach. Data will be organized hierarchically, with within-person/random EMA prompts across the study period nested within people. Random (within-person) coefficients will be estimated for each person at Level 1, while fixed (between-person) coefficients will be estimated at Level 2. Within-person variables will be centered at Level-1 and between-person variables will be grand mean centered at Level-2⁸⁸⁻⁹⁰. We will examine associations between [e.g., attributions] and [e.g., number of interactions] at Level 1, and fit models with fixed [e.g. group, age, gender] main effects at Level 2. We will also examine [L1] and [L2] cross-level interactions.

Analysis of Social Interaction Skills (Aim 3) and Durability (Aim 4): The secondary outcome social interaction skills, assessed by SSPA, will be compared between USS and control using a repeated measures linear mixed model similar to that described in the analysis of the primary outcome. Durability will also be compared between USS and control using the mixed model. For primary and secondary outcomes, linear contrasts will be used to estimate intervention group differences and 95% confidence intervals at the 2-month FU assessment.

Analysis of Mediation (Exploratory Aim A): We will explore content learning (USS Skills Test) as a potential mediator of the relation between intervention and changes in social functioning. Direct and indirect effects will be estimated using a structural equation model. Mediation (i.e. indirect effects) will be tested using the bootstrapping approach⁹¹.

Analysis of Moderation (Exploratory Aim B): Heterogeneity of treatment effects (HTE) for the primary outcomes will be explored in subgroups of participants based on baseline characteristics including cognition, symptom clusters, illness characteristics, medication dose (chlorpromazine equivalents) and demographic variables. These subgroup analyses are aimed at determining whether there is differential effectiveness of the interventions among participant subgroups. Evidence of HTE will be based on tests of interaction within the longitudinal model structure described above.

Interim Monitoring: Interim monitoring will focus on safety, recruitment, adherence to protocol, baseline comparability of intervention groups, completeness of data retrieval, and uptake of the assigned intervention. A set of monitoring tables will be generated for this purpose. No interim monitoring for efficacy or futility is being proposed.

Analysis of social function between the psychotic spectrum and normative psychiatric sample: Multilevel modeling will be used to examine the predictive ability of social rewards on later social motivation and compared between the psychosis spectrum and normative samples. To examine the frequency of negative appraisals of social interactions and their predictive ability, and to compare this information between psychotic and normative samples, two models will test the effect of group (PSD/control) on social rewards (model 1) and negative social appraisals (model 2). Additional multi-level models will examine desire for socialization and initiation of future social activity. In each model, group, social reward, and the group-by-social-reward interaction will be included as predictor variables. Similar models predicting desire for socialization and initiation of future social activity will be computed with group, negative social appraisal, and their interaction as the predictor variables.

Plan for Missing Data: Several strategies will be imposed to accommodate the likelihood that missing data will occur during this study. Prevention is the most obvious and effective manner to control bias and loss of power from missing data⁹². Prior to the trial we will pilot data collection procedures. Variables with large proportions of missing data will be excluded from collection. We will follow the intent to treat principle, requiring follow-up of all participants randomized regardless of the treatment received⁹³. Regular data entry into case report forms (CRFs) combined with monitoring and missing data reports will trigger protocols for tracking and obtaining missing data. Despite these prevention efforts it is reasonable to assume missing data will occur. Our proposed primary and secondary analyses make use of all available data and are valid under the assumption that missing data will be missing at random (MAR)^{86, 94}. We will evaluate the plausibility of this assumption by determining the extent of missing data and use logistic regression to identify factors associated with missing data. We will conduct sensitivity analysis using a pattern-mixture approach implemented using multiple

imputation under missing not at random (MNAR) assumptions to examine the robustness of conclusions of the primary analysis to missing data^{86, 92}.

6. References:

1. World Health Organization. Schizophrenia: Fact sheet No 397.; Sept 2015.
2. National Institutes of Mental Health. [Archive Material] Translating behavioral science into action: report of the national advisory mental health council behavioral science workgroup; 1999.
4. American Psychiatric Association TFoD-V. Diagnostic and statistical manual of mental disorders, fifth edition. Arlington, VA: American Psychiatric Association; 2013.

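### The psychosis-versus-control EMA models have no calendar-period term, so this non-randomised comparison is open to era bias if the two samples were observed at different times

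*Combined protocol and SAP*

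**What the plan says.** The COVID-19 Pandemic Procedures section of the protocol makes the way the study is run depend on the period: "As long as COVID-19 remains a significant concern, this study will conduct the majority of research procedures remotely, via VA-approved telehealth platforms". The rule covers everyone recruited during the pandemic. Training sessions can also take place by video or in person.

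The Participants section plans about 120 randomised Veterans with psychosis and about 20 psychiatric controls. The controls are not randomised and contribute one 7-day EMA week, with the same questions as the psychosis sample. No section says when the controls are recruited, or that their EMA weeks should overlap in time with those of the psychosis sample.

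The SAP section on social function in the psychotic spectrum and normative samples sets out two models for the effect of group on social rewards and on negative appraisals. Further models address desire for socialization and initiation of social activity. Of these it says: "In each model, group, social reward, and the group-by-social-reward interaction will be included as predictor variables". A parallel set puts negative appraisal in place of reward. No covariate is listed.

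For the randomised comparison, Analysis of Primary Outcome SFS (Aim 1) says: "The mixed model will include fixed effects for intervention (USS vs. active control), time (mid, post, FU), and the interaction of intervention with time". Baseline SFS is added as a further fixed effect. Randomization is stratified by baseline SFS only.

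**The concern.** The EMA asks how often and how people interact, how much they enjoy it and what they expect of future interactions. A period that limits contact could plausibly shift these answers whatever the diagnosis. If one sample was observed more under pandemic conditions than the other, the group coefficient would combine diagnosis and era, and an era difference could be reported as a feature of psychosis. Nothing in the design guards against this: there is no randomisation between the samples, no matching on date and no covariate. With about 20 controls, each giving a single week, the result depends heavily on when those 20 were recruited.

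**Working it through.** **Inputs from the documents.** About 120 psychosis participants and about 20 controls (Participants). SFS SD 13.1, target difference 9 points, 90% power, two-sided 0.05, 1:1 allocation (Justification of Sample Size). The plan gives no power or precision figure for the psychosis-versus-control comparison.

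**Assumptions, none given in the documents.** An era effect of 0.3 to 0.5 SD on a person's mean reward or appraisal. A difference in era share between the samples of 0, 25 or 50 percentage points. One baseline EMA mean per person, with equal variance in both groups. For the SFS: half the sample in each era, a shift of 3 to 9 points, and a baseline-to-post correlation ρ of 0.5 to 0.7.

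**Step 1. The plan's own figure.** The plan says "a sample size of 46 subjects per group will be required to detect a 9 point difference". The normal approximation gives 45 per group. With the noncentral t, power is 89.7% at 45 and 90.3% at 46, so 46 reproduces. Allowing for dropout, 92 / 0.80 = 115, which the planned 120 covers.

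**Step 2. Group comparison without an era term.**
- SE = √(1/120 + 1/20) = 0.2415 SD.
- Bias = era effect × difference in era share.
- False-positive rate = P(|Z + bias/SE| > 1.96).

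| Difference in era share | Era effect (SD) | Bias (SD) | False-positive rate |
|---|---|---|---|
| 0 points | any | 0 | 5% |
| 25 points | 0.3 | 0.075 | 6.1% |
| 25 points | 0.5 | 0.125 | 8.1% |
| 50 points | 0.3 | 0.15 | 9.5% |
| 50 points | 0.5 | 0.25 | 17.9% |

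**Step 3. Cost of the era term.** Take half of the psychosis sample in each era (60 and 60) and all 20 controls in one era, which is the 50-point case. The squared correlation between group and era is (60×20 − 60×0)² / (120×20×60×80) = 0.125. The SE becomes 0.2415 / √(1 − 0.125) = 0.258 SD. Comparing the 60 same-era psychosis participants with the 20 controls gives the same value: √(1/60 + 1/20) = 0.258. If the controls are spread over both eras, the correlation and the cost are smaller.

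**Step 4. The SFS contrast.** With s² = 13.1² = 171.61 and half the sample in each era, a shift of δ points adds V = δ²/4 to the variance. If a participant's mode is the same at every visit, V enters both baseline and post, and the residual variance after adjusting for baseline is (s² + V) − (ρs² + V)² / (s² + V), against s²(1 − ρ²) with no shift.
- δ = 3, V = 2.25: 129.26 against 128.71 (ρ = 0.5), +0.4%; 87.72 against 87.52 (ρ = 0.7), +0.2%.
- δ = 9, V = 20.25: 133.24 against 128.71 (ρ = 0.5), +3.5%; 89.15 against 87.52 (ρ = 0.7), +1.9%.

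The loss is therefore 0.2% to 3.5% of residual variance.

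**The case against.** The era effect and the imbalance are both assumed. The Recruitment section describes recruiting Veterans with and without psychosis together from the same outpatient clinics, so the samples may well overlap in time. That stands: the documents do not show that bias is present, only that nothing prevents it.

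Visit mode is not a route to bias in these models, because both samples answer the same questions by smartphone. That stands too, and it limits the point to calendar period.

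The error rates in Step 2 apply to group differences in person means. They do not carry over directly to the terms for reward or appraisal predicting later behaviour, or to the group interactions. This is also an additional, descriptive aim and not an efficacy test. Both points stand, and they make this a minor matter.

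A reader might go further and infer that the primary SFS result is compromised. The documents do not support that. Concurrent 1:1 allocation in permuted blocks keeps the arms roughly balanced over calendar time, so era does not bias the contrast. A reader might also put the precision loss at 2% to 23% of residual variance by adding the whole of V to s²(1 − ρ²). That is right only if the shift affects post and leaves baseline untouched. For a participant whose mode stays the same, the baseline SFS covariate absorbs most of the shift. The pandemic rule is worded partly by calendar and partly by recruitment date, so a change of mode between visits is possible, but the documents do not show it to be common. Even with a 9-point shift at post only, power for 9 points at 46 per group is 93.8% to 98.4% over the same correlations, above the planned 90%.

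**Conclusion.** The gap is real but narrow. The psychosis-versus-control models contain no calendar-period term, recruitment includes a pandemic period, and the two samples need not be contemporaneous. If era shares differ by 50 points and the era effect is 0.3 to 0.5 SD, a person-mean group difference is biased by 0.15 to 0.25 SD and the false-positive rate is 9.5% to 18%. At a 25-point difference the rate is 6% to 8%, and with equal shares there is no bias. All of this rests on an era effect and an imbalance that the documents do not give.

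For the randomised SFS contrast there is no bias, and any loss of precision is small when mode is constant within a person. The sample size and the primary model can stay as they are.

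**What to change.** 1. In the SAP section on the psychotic spectrum and normative samples, add the calendar period of the EMA week, taken from the survey dates, as a covariate in the group models. Fix the cut date before the EMA data are examined.
2. Add a sensitivity analysis restricted to psychosis participants whose baseline EMA week falls in the same calendar period as the controls'. Report the distribution of EMA dates by sample. If the samples do not overlap in time, neither analysis can separate group from era, and the report should say so.
3. For the SFS, record the mode of each assessment and add a sensitivity analysis that takes it into account. No mode or era terms are needed in the primary model. A term fixed at randomisation would in any case miscode participants who change mode later, and they are the ones who could cause a material loss.

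The cost is SAP wording and one recorded field per SFS visit, since the survey dates already exist. Precision in the group comparison falls slightly (SE from 0.24 to at most 0.26 SD with half of the psychosis sample in each era), and the sensitivity analysis uses a smaller psychosis sample.
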